5.5.2. Pharmacodynamics

The pharmacodynamic (PD) marker evaluated in this study is Total lymphocyte counts, which were measured as part of the clinical laboratory hematology tests.

The following parameters are collected:

- Absolute count in peripheral blood lymphocyte counts as a function of ponesimod dose and plasma concentrations at trough level (pre-dose) on Days 8 and 15 (Visits E2 and E3) and at Visits E4, E7, E9, E13 (EOT2), P2, P7, P14, P22, P30 and EOT3, as applicable.
- Post-treatment lymphocyte recovery 8, 30, and 90 days (only at 90 days for patients performing TP2 and TP3, if applicable) after study drug discontinuation.

The following summaries for peripheral blood lymphocyte counts as a function of ponesimod dose, as described in Section 5.4.5.1, will be produced:

- Summary of absolute values and absolute change from ponesimod baseline values for lymphocyte counts: descriptive statistics by analysis visit (AP3 on the PAS);
- Summary of percent change from ponesimod baseline values for lymphocyte counts: descriptive statistics by analysis visit (AP3 on the PAS);

In addition, the following plot, as described in Section 5.4.5.1 will be produced:

• Plot of percent change from ponesimod baseline values for lymphocyte counts: mean ± SE by analysis visit (AP3 on the PAS);

The following summaries for post-treatment lymphocyte count recovery, as described in Section 5.4.5.1, will be produced:

- Summary of absolute values at ponesimod baseline, at last on-treatment and at each followup visits (FU7, FU30, FU90 and Last FU)) for lymphocyte counts (completed/discontinued subjects with at least one follow-up value only): descriptive statistics (AP3 on the PAS); by Post-Treatment DMT subgroup ((Any DMT, including ponesimod), No DMT).
- Summary of percent change from ponesimod baseline to last on-treatment and to each follow-up visit (FU7, FU30, FU90 and Last FU)) for lymphocyte counts (completed/discontinued subjects with at least one follow-up value only): descriptive statistics (AP3 on the PAS); by Post-Treatment DMT subgroup ((Any DMT, including ponesimod), No DMT).

In addition, the following plots, as described in Section 5.4.5.1, will be produced:

- Plot of absolute values at ponesimod baseline, at last on-treatment and at each follow-up (FU7, FU30, FU90 and Last FU)) for lymphocytes (completed/discontinued subjects with at least one follow-up value only): mean ± SE (AP3 on the PAS); by Post-Treatment DMT subgroup ((Any DMT, including ponesimod), No DMT).
- Plot of percent change from ponesimod baseline to last on-treatment and follow-up visits

(FU7, FU30, FU90 and Last FU)) for lymphocytes (completed/discontinued subjects with at least one follow-up value only): mean \pm SE (AP3 on the PAS); by Post-Treatment DMT subgroup ((Any DMT, including ponesimod), No DMT).

5.5.3. Pharmacokinetic/Pharmacodynamic Relationships

The following endpoint, "Efficacy and safety parameters will be correlated with absolute lymphocyte counts and magnitude of reduction of lymphocyte counts on an exploratory basis." was added to explore the objective: dose response relationship of 10, 20, and 40 mg ponesimod on lymphocyte count, magnetic resonance imaging (MRI) endpoints, annualized relapse rate (ARR), and safety endpoints.

Analyses to address dose decisions were presented in the Interim Analysis CSR and are not planned to be addressed in the Final CSR.

5.5.4. Biomarkers

Not applicable

5.5.5. Health Economics

Not applicable

5.5.6. Definition of Subgroups

The following subgroups are defined for the Follow-up Phase:

- (i) Post-treatment DMT: A patient in the Follow-up Phase is assigned to the "Any DMT, including ponesimod" category if there is a record in CMDECOD in SDTM.CM for any of the therapies listed in Table 11 in Section 6.5.1 and the corresponding CMENDTC in SDTM.CM is on or after the ponesimod EOT date or ongoing at EOS date. In cases where CMENDTC is missing and CM is not ongoing, it should be checked whether CMSTDTC is on or after the ponesimod EOT date. Otherwise, the patient is assigned to the "No DMT" category.
- (ii) Total Exposure Duration: A patient in the Follow-up Phase is assigned to one of the following categories "Less than or equal to 4 years", "Greater than 4 and Less than or equal to 8 years", "Greater than 8 years", based on their Ponesimod exposure duration during AP3 (years), as defined in Table 10 in Section 5.4.1.1. This subgroup will be considered only for PFT.

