3.11.5.3 Concomitant medications

All medications taken by the patient from the beginning of the transition period until EOS2 or EOS3, i.e., all medications ongoing, started or stopped during this period, will be recorded on the Concomitant Medications form of the extension eCRF.

Commercially available ponesimod may be initiated on the day following last intake of study treatment. The start date of commercially available ponesimod must be recorded on the Concomitant Medication form of the eCRF.

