5.3.2.2. ARR in the Post-treatment-emergent Period

Summary statistics are presented for ARR in the post-treatment-emergent period, as defined in Section 5.3.1.4.

The following summary is presented for the Post-Treatment DMT subgroup (Any DMT, including ponesimod), No DMT)), where the Post-Treatment DMT subgroup is defined in Section 5.5.6 and the list of DMTs is provided in Table 11 in Section 6.5.1.

- Number of confirmed relapses per subject: descriptive statistics;
- Number of confirmed relapses per subject: frequency counts and percentages for categories 0, 1, 2, 3, 4, and 5+;
- Total number of confirmed relapses: sum;
- Total time in Analysis Period (subject years): sum;
- Raw ARR: total number of confirmed relapses/total time in Analysis Period;

This table is also presented for all relapses.

A listing of confirmed/all relapses in this period is also presented.

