5.4.4.3.3. Post-treatment-emergent adverse events

The following summaries are presented:

- Post-treatment-emergent AEs by SOC and PT (frequency; AP3 only, completed/discontinued subjects only).
- Post-treatment-emergent AEs by SOC and PT (frequency; AP3 only, completed/discontinued subjects only) by Treated (DMTs, including ponesimod), Not treated and Total.

A listing of all post-treatment AEs is provided based on the PAS.

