AC- 058B201 CSR SAP section 6.4.3.1	The EDSS assessment used for confirmation of disability accumulation must not be during a relapse. In the event of a missing relapse end date, the core study report considered relapse start date + 30 days. This SAP uses relapse start date + 90 days.	This derivation is updated to be in-line with the deviation as used in the Phase 3 program.
Section 5.1.3	Definition of Treatment emergent adverse events and other safety variables.	Definition updated to exclude pregnancy interruption period(s).
Various Sections	Disposition will include a new category corresponding to "Approved drug available for indication".	New reason in aCRF p.9 (Trial disposition) and p. 11 (Discontinuation of Study Treatment): "Approved drug available for indication".
Section 5.4.5.4		Echocardiogram: Criteria for defining abnormality have changed subsequent to 2019 IA and are reflected in the SDTM data.
Section 5.1.7	Coding Dictionaries: MedDRA Version 26.0 and WHO-Drug Dictionary version March 2023 B3G will be used.	Up-versioning to current dictionaries.
Section 5.1.3	Added Planned Pregnancy Interruptions: - excluded for definition of exposure, treatment-emergent adverse events and other safety variables. - not excluded for efficacy analyses or for study duration.	This rule was adopted for the Snapshot Analysis in 2022 and will be retained for the Final CSR.
Section 5.1.6	Added Definition: The post-treatment- emergent period.	This period was added to address analyses pertaining to relapses in Section 5.3.1.4 and for AEs in Section 5.4.4.3.3.

Section 5.1.8	Added additional Visit Windows	Added to cover the entire study period.
Section 5.2.1.3	Added Definition: Entered Follow-up Phase.	This definition is required for the identification of patients in the DMT subgroups.
5.2.2	Display of Subject Disposition: Kaplan- Meier plot for time to premature treatment discontinuation will not be presented.	This was presented in the Interim Analysis CSR and will not be presented in the Final CSR.
5.3.1.2	Removed Analyses for the endpoint: ARR up to last treatment in the Analysis Period + 7 days will not be performed.	This was presented in the Interim Analysis CSR and will not be presented in the Final CSR.
5.3.1.4	Added endpoint in Section 5.3.1.4: Annualized relapse rate in the Post- treatment-emergent period. Added planned analyses for this endpoint in Section 5.3.2.2.	This was added to assess disease reactivation.

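### The post-treatment category that counts ponesimod as a DMT mixes patients who never stopped the drug with patients who switched, so that column cannot show reactivation or recovery after stopping

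*SAP*

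**What the plan says.** SAP 5.5.6 names the first class "Any DMT, including ponesimod" and sets the rule for it: "A patient in the Follow-up Phase is assigned to the 'Any DMT, including ponesimod' category if there is a record in CMDECOD in SDTM.CM" for a therapy listed in Table 11, provided that therapy ended on or after the ponesimod end-of-treatment date or was ongoing at end of study. A start-date check covers missing end dates. Everyone else falls into the second class: "Otherwise, the patient is assigned to the 'No DMT' category". Table 11 (SAP 6.5.1) lists ponesimod beside ocrelizumab, natalizumab, cladribine, the interferons and others.

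Protocol 3.11.5.3 lets patients carry on with the drug: "Commercially available ponesimod may be initiated on the day following last intake of study treatment". It also requires that "The start date of commercially available ponesimod must be recorded on the Concomitant Medication form of the eCRF", so the concomitant-medication rule will pick these patients up. Protocol 3.12.4 keeps them in the safety follow-up visits, timed from the last study-drug dose whatever commercial drug they take. SAP 5.1.6 starts the post-treatment period 16 days after the last dose of ponesimod given as study drug.

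The two classes are then used in:
- the post-treatment ARR (SAP 5.3.2.2: "The following summary is presented for the Post-Treatment DMT subgroup"), whose purpose SAP 6.2.3 gives as "This was added to assess disease reactivation";
- post-treatment adverse events (SAP 5.4.4.3.3: "by Treated (DMTs, including ponesimod), Not treated and Total");
- lymphocytes at follow-up (SAP 5.4.5.1 and 5.5.2, the latter presenting them as recovery outputs);
- pulmonary function at follow-up (SAP 5.4.5.5).

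**The concern.** A patient who takes commercial ponesimod the day after the last study tablet has not stopped ponesimod, yet counts as post-treatment and shares a column with patients who did stop and were given something else. These tables are there to show what happens when the drug is withdrawn. A continuer cannot contribute to that: no withdrawal has occurred, the lymphocyte count should stay reduced, and any drug effect on lung function should persist. Pooling can hide reactivation among switchers, and it yields lymphocyte and lung-function means that describe neither continued treatment nor recovery.

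Continuing on commercial supply is a planned route out of the study. SAP 5.2.1.5 counts it as treatment completion and SAP 5.2.2 shows it separately in the disposition tables. No planned summary of outcomes separates it.

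**Working it through.** The plan gives no figure for this subgroup, so there is none to reproduce. The check is a simple mixture.

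**Formula.** Column value = f × (value in continuers) + (1 − f) × (value in switchers). Here f is the continuers' share of the column: of follow-up time for the raw ARR, of patients for lymphocytes. The documents do not give f, so it is varied.

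**ARR.** Continuers: 0.15, the long-term 20 mg estimate in Protocol 1.3.2.3. Switchers: 0.30 to 0.50, assumed.

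| f | switchers 0.30 | switchers 0.50 |
|---|---|---|
| 10% | 0.1×0.15 + 0.9×0.30 = 0.285 | 0.1×0.15 + 0.9×0.50 = 0.465 |
| 50% | 0.5×0.15 + 0.5×0.30 = 0.225 | 0.5×0.15 + 0.5×0.50 = 0.325 |
| 80% | 0.8×0.15 + 0.2×0.30 = 0.18 | 0.8×0.15 + 0.2×0.50 = 0.22 |

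At 10% the column is close to the switchers' own rate. At 80% it is close to the continuers' rate.

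The column alone cannot tell these situations apart. A pooled 0.225 arises from f = 50% with switchers at 0.30. It also arises from f = (0.50 − 0.225)/(0.50 − 0.15) = 79% with switchers at 0.50.

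**Lymphocytes.** Continuers: a 65.3% mean reduction at 20 mg (Protocol 1.3.2.2, core study Week 24). The switchers' value is unknown. Protocol 1.3.2.2 says counts generally return to the normal range within a week off ponesimod. However, Table 11 includes fingolimod, siponimod and ozanimod, which Protocol 1.2 describes as S1P receptor modulators, so some switchers may stay suppressed. Two assumed values:

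| f | switchers 0% | switchers 20% reduction |
|---|---|---|
| 10% | 0.1×65.3 = 6.5% | 6.5 + 0.9×20 = 24.5% |
| 50% | 0.5×65.3 = 32.7% | 32.7 + 0.5×20 = 42.7% |
| 80% | 0.8×65.3 = 52.2% | 52.2 + 0.2×20 = 56.2% |

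If switchers were as suppressed as continuers, the column would read 65.3% at any f.

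**How much relapse data there is.** After treatment periods 2 and 3 the nominal window runs from day 16 to day 90: 75 days, or 75/365.25 = 0.205 years. After treatment period 1 it runs from day 16 to day 30: 15 days, or 0.041 years. For illustration, 100 patients at 0.15 over 75 days give 100 × 0.205 × 0.15 ≈ 3.1 relapses; 20 switchers at 0.30 give 20 × 0.205 × 0.30 ≈ 1.2.

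**The case against.** The best defence is that the split is openly one of treated against untreated after study drug, and the untreated column is the direct read-out of reactivation and recovery. That stands. A reader might infer that the post-treatment tables as a whole cannot be interpreted. The documents do not support that, because patients with recorded commercial ponesimod are kept out of No DMT. The pooled column also remains a valid description of patients with some recorded DMT.

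A reader might also infer that continuers dominate the column. Nothing in the documents says so. SAP 5.2.1.5 lists availability of commercial ponesimod for treatment period 3 only, and the study began in 2010. Patients who stopped in an earlier period, or before approval in their country, are not continuers by this route. At a low share little is masked.

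A third tempting inference, that switchers' lymphocytes return to baseline, fails because other S1P modulators are on the list.

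Three further points have weight. Relapses will be few, so a table could not reliably separate 0.18 from 0.30. The post-treatment ARR is descriptive, with no model or interval, in a study whose objectives are all exploratory. Planned listings of relapses, post-treatment adverse events, lymphocyte values and flagged therapies allow partial reconstruction by patient. They do not supply denominators, follow-up time or rates by group, and for pulmonary function only outliers and positive bronchodilator tests are listed.

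Finally, an other-DMT level would itself be mixed. That limits what the fix delivers, but it is no reason to keep patients still on ponesimod among those who left it.

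**Conclusion.** The point holds within limits. The pooling is explicit in the category and in Table 11, and no planned outcome summary undoes it. The column that counts ponesimod as a DMT cannot show disease reactivation, lymphocyte recovery or lung-function recovery after stopping ponesimod. No DMT can, for the selected group who received nothing else.

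The size cannot be fixed from the documents. It ranges from slight at a 10% share of continuers to near-complete masking of the switchers' ARR at 80%. The shares, the switchers' ARR and the switchers' lymphocyte values are all assumptions; only the on-ponesimod values come from the protocol. This is a reporting weakness in exploratory, descriptive outputs, worth correcting because the correction is cheap. It does not touch the main on-treatment analyses.

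**What to change.** In SAP 5.5.6, split the flag into three levels: commercial ponesimod after end of treatment, other DMT, and no DMT. State how a patient with both commercial ponesimod and another DMT is assigned. Use the three levels, with the number of patients and follow-up time in each, in SAP 5.3.2.2, 5.4.4.3.3, 5.4.5.1, 5.4.5.5 and 5.5.2. The present pooled column may stay as a total. In the lymphocyte outputs, identify patients on other S1P modulators, and read the other-DMT level descriptively.

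The cost is one extra level on a flag already derived from the coded medication name, with no new data collection. The price is smaller cells, few relapses per cell, and an other-DMT level that remains heterogeneous.

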3.12.5 Unscheduled visits

3.12.5.1 Unscheduled relapse visit

Patients will be instructed to contact their treating neurologist at the clinical site immediately in the event of appearance of any symptoms suggestive of an MS exacerbation. An unscheduled visit will be organized as soon as possible after onset or worsening of the symptom(s) as follows:

The primary investigator / treating neurologist will examine the patient and decide whether the patient has to be referred to the evaluating neurologist.

In the event of the patient's referral to the evaluating neurologist, the evaluating neurologist will perform the EDSS and FS within 7 days after onset or worsening of the symptom(s).

In order to exclude potential other reasons for the symptom(s) observed, the primary investigator / treating neurologist will need to perform the following assessments:

- Physical examination;
- Vital signs: SBP/DBP, pulse rate, body temperature.

Results must be documented in the patient's records, but should not be recorded in the CRF, unless a finding constitutes an AE.

The decision regarding whether the neurological change is considered as confirmed or unconfirmed relapse will be made by the primary investigator / treating neurologist based on the EDSS/FS scores assessed by the evaluating neurologist.

A Specific Relapse eCRF form must be completed for confirmed and unconfirmed relapses. MS relapses and associated symptoms are not to be entered on the AE form of the eCRF with the following exceptions:

- MS relapses with fatal outcome (these must always be recorded as an AE on the AE form in addition to being reported as SAEs).
- MS relapses that, in the view of the investigator, warrant specific notice due to unusual frequency, severity or remarkable clinical manifestations (these should be reported as an AE on the AE form of the eCRF and, if applicable, on the SAE form).

If a relapse visit is within 5 days prior to the date of a regular MRI visit, efforts should be made to perform the MRI assessments prior to the start of treatment with i.v. corticosteroids.

In the event of a confirmed MS relapse, the primary investigator / treating neurologist should re-counsel the patient to ensure she/he is reminded of alternative treatment options available for RRMS. The patient's attention must be drawn to the possibility of

Ponesimod / ACT-128800 / JNJ-67896153 Multiple Sclerosis		EudraCT 2009-011470-15 EDMS-ERI-206617631
Protocol AC-058B202	Confidential	
Version 12		

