5.1.6. Post-treatment-emergent definition

The post-treatment-emergent period is defined as follows:

The start date of the period is the date of last administration of ponesimod as study drug plus 16 days (inclusive). See Section 5.1.4 for the definition of treatment-emergent, which is defined as the time from first administration of ponesimod up to 15 days (inclusive) after last administration of ponesimod as study drug.

The end date of the period is last study date [see Section 5.1.1].

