5.3.1.4. Annualized relapse rate in the Post-treatment-emergent period

The following variables are derived for the analysis of ARR in the post-treatment-emergent period:

- Number of confirmed/all relapses with start date in the post-treatment emergent period; i.e. date of last administration of ponesimod plus 16 days, as defined in Section 5.1.6;
- Length of observation for the post-treatment-emergent period as defined in Section 5.1.6, expressed in years.

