6.5. Appendix 5 Prior and Concomitant Medications

Previous and concomitant medications/therapies are stored in the SDTM.CM datasets. The two CM datasets SDTM201.CM and SDTM202.CM are concatenated for the purposes of this analysis. Terms are coded using the World Health Organization (WHO) drug code dictionary and the anatomic therapeutic chemical (ATC) class code (version dated September 2021 B3G).

A previous therapy is any treatment for which the end date of treatment is prior to the first dose of ponesimod (including medications with an end date in the core study for patients originally randomized to placebo).

Treatment-concomitant therapies are all treatments that are ongoing or initiated after first dose of ponesimod, or that were initiated up to the end of ponesimod treatment.

Post-treatment therapies are those which were initiated after the end of ponesimod treatment, i.e after the ponesimod EOT date as described in Section 5.1.1

Where start date of medication/therapy is missing or partial, the following medications/therapies are considered to be previous therapies:

- Medication end date is not missing and is < ponesimod treatment start date;
- If day is missing and the month/year of the medication end date is < month/year of the ponesimod treatment start date;
- If day and month are missing and the year of the concomitant medication end date is < year of treatment start date.

Otherwise, the medications/therapies with missing or partial start date are considered as treatmentconcomitant. Medications considered treatment-concomitant where there is a possibility that they are previous will be flagged in listings, for example, if day is missing and month and year are same as month and year of ponesimod start date.

Beta blocking therapies will be listed for the pooled B201/B202 studies. Beta blocking agents are defined as medications with WHO-Drug anatomic therapeutic chemical (ATC) class level 2 code C07: BETA BLOCKING AGENTS". This is a sub-class of ATC class C "Cardiovascular system". Steroids used for the treatment of relapses are selected in SDTM.CM using CMCAT="CORTICOSTEROIDS (IV) FOR TREATMENT OF RELAPSE".

Covid-19 vaccines are selected in SDTM.CM using CMCLASS = "COVID-19 VACCINES".

Assignment as prior, treatment-concomitant, and post-treatment therapy is derived using the definitions above.

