VISITS				Day 1 of re- initiatio n	Day 15 of re- initiatio n	Unscheduled visit after drug interruption for planned pregnancy	Unscheduled visit prior to study drug re-initiation after interruption for planned pregnancy	Unscheduled visit for re-initiation of study drug following study drug interruption for planned pregnancy	Unscheduled visit for re-initiation of study drug following study drug interruption for planned pregnancy
	Time	Any day between Day 1 and FU3 (EOS3)		Any day between Day 1 and EOT3		30 days after study drug interruption for planned pregnancy	30 days (±5 days) before study drug re-initiation		

CONFIDENTIAL – FOIA Exemptions Apply in U.S.

Status: Approved, Date: 20 September 2023

JNJ-67896153/ACT-128800 (Ponesimod)

Statistical Analysis Plan AC-058B202

	Visit window	+ 7 days	NA	NA	±1 day	±7 days	NA	NA	NA
EDSS / F	unctional	Х	Х			Х	Х		
Systems ¹	.6								
* Chest X	(-ray								
* MRI			Х			Х	Х		
Concom	itant	Х	Х	Х	Х	Х	Х	X ¹⁹	Х
medicati	ons								
* Physica	al	Х	X ⁵			Х	Х		
Examinat	tion								
Systolic	/diastolic	Х	Х	Х	Х	Х	Х	Х	Х
blood pro	essure ⁶								
* 12-lead	I ECG ⁶		Х	Х	Х	Х	Х	Х	Х
Ophtha	Imologic		Х			Х	Х		
examinat	tion ⁸								
Pulmon	ary		х			Х	Х		
function	tests ⁹								
*			х			Х	Х		
Hematol	ogy/Blood								
chemistr	у								
* Urinaly	sis		Х			Х	Х		
* Pregna	ncv Test ¹⁸		х			Х	X (first	X (first	
							assessment)	assessment)	
* Study D	Drug		Х	Х	Х			X ¹⁹	Х
Dispensi	ng/Return								
Adverse	e Events	Х	Х	Х	Х	Х	Х	Х	Х
Serious	Adverse	Х	х	Х	Х	Х	Х	Х	Х
Events									

Note: The footnotes apply to Table 15, Table 16, Table 17 and Table 18.

*Data are not collected in the CRFs (unless a finding constitutes an AE or SAE), except for body weight (see footnote 5). For MRI and echocardiography only the date of assessment is collected in the CRFs.

- All Week 24 (EOT) assessments of the core study (AC-058B201) must be completed prior to randomization in the extension study. If a
 patient is going to enter the extension study the Visit E1 should be scheduled within 3 days after the Week 24 (EOT) visit of the core study.
 Patients will have to continue using their core study medication every day until and including the day prior to Visit E1.
- 2. Phone call: The site will call the patient for information on health status / adverse events.

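### The post-treatment relapse rate by DMT subgroup uses one ever/never label per patient and ignores whether the DMT began before or after the relapse, so the 'No DMT' rate is biased down if relapses lead to DMT starts before end of study.

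*SAP*

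**What the plan says.** - **Label (SAP 5.5.6).** Each patient in the Follow-up Phase gets one Post-treatment DMT category. 'Any DMT, including ponesimod' applies if a Table 11 therapy is recorded and "the corresponding CMENDTC in SDTM.CM is on or after the ponesimod EOT date or ongoing at EOS date". The medication start date is consulted only when the end date is missing and the therapy is not ongoing, and then only against ponesimod EOT. All other patients are 'No DMT'.
- **Period (SAP 5.1.6).** It starts 16 days after the last dose. For its close, "The end date of the period is last study date".
- **Numerator and denominator (SAP 5.3.1.4).** All relapses with onset in the period are counted. The denominator is "Length of observation for the post-treatment-emergent period as defined in Section 5.1.6, expressed in years".
- **Display (SAP 5.3.2.2).** By DMT subgroup: "Raw ARR: total number of confirmed relapses/total time in Analysis Period". The bullets say Analysis Period where 5.3.1.4 defines the post-treatment-emergent length of observation. That is an editorial slip only.
- **Purpose (SAP 6.2.3).** "This was added to assess disease reactivation".
- **Route from relapse to DMT (Protocol 3.12.5.1).** After a confirmed relapse the investigator "should re-counsel the patient to ensure she/he is reminded of alternative treatment options available for RRMS". Unscheduled relapse visits are allowed up to FU3 (SAP Table 18), and medications are recorded until EOS2 or EOS3 (Protocol 3.11.5.3).

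**The concern.** Subgroup membership is fixed by something that can happen after the outcome. Take a patient who stops ponesimod, relapses untreated, and starts a DMT before end of study. The relapse and all the untreated time before it are counted in 'Any DMT'. 'No DMT' loses a relapse that occurred off drug and keeps the patients who did not relapse, or who relapsed without a recorded DMT start.

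If relapse raises the chance of starting a DMT before end of study, the 'No DMT' rate is too low and the 'Any DMT' rate too high. The endpoint was added to look for reactivation after stopping, so the error runs towards making reactivation look smaller. Patients who begin commercial ponesimod the day after the last dose are labelled correctly. Corticosteroids are not in Table 11, so steroid treatment of a relapse does not by itself change the label.

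**Working it through.** The plan states no post-treatment ARR, sample size or precision for this table, so there is no figure to reproduce. The check is of what the definition does.

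**Inputs from the documents.** Follow-up is 90 days after the last dose in TP2/TP3 and 30 days in TP1 (Protocol 3.1.1). Counting starts at day 16, so the window *W* is 90 − 16 + 1 = 75 days, or 30 − 16 + 1 = 15 days.

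**Assumed inputs (not in the documents).** *q* is the share of off-drug relapses that lead to a DMT. *d* is the delay in days from relapse to DMT start. Relapses follow a Poisson process.

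**Formula.** A relapse drops out of 'No DMT' if it triggers a DMT and at least *d* days of the window remain. Hence

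'No DMT' ARR ÷ true off-drug rate = 1 − *q* × max(0, *W* − *d*)/*W*

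The off-drug rate itself cancels. Example: *q* = 25%, *d* = 14, *W* = 75 gives 1 − 0.25 × 61/75 = 0.80.

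**90-day follow-up, ratio to the true off-drug rate:**

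| *q* | *d* = 0 | 14 | 28 | 42 | 56 | 70 |
|---|---|---|---|---|---|---|
| 0% | 1.00 | 1.00 | 1.00 | 1.00 | 1.00 | 1.00 |
| 10% | 0.90 | 0.92 | 0.94 | 0.96 | 0.97 | 0.99 |
| 25% | 0.75 | 0.80 | 0.84 | 0.89 | 0.94 | 0.98 |
| 50% | 0.50 | 0.59 | 0.69 | 0.78 | 0.87 | 0.97 |
| 75% | 0.25 | 0.39 | 0.53 | 0.67 | 0.81 | 0.95 |

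**30-day follow-up (TP1).** With *d* = 14 and *q* = 75% the ratio is 1 − 0.75 × 1/15 = 0.95. With *d* = 7 it is 0.95, 0.87, 0.73 and 0.60 for *q* = 10, 25, 50 and 75%.

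**Simulation.** Assumptions: 0.60 relapses per year off drug, 0.20 on a DMT, and half the patients on a DMT from Day 1. The ratios agreed with the formula to about 0.01. With 90-day follow-up and *d* = 14, the 'Any DMT' ARR (true value 0.20) came out at 0.25, 0.32, 0.43 and 0.52 for the four values of *q*. The order of the two subgroups reversed only at *q* = 50% with *d* = 0 or 14, or at *q* = 75% with *d* = 0, 14 or 28. Splitting person-time at DMT start returned 0.59–0.60 off drug throughout.

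A separate simulation used an off-drug rate of 0.40 and delays of 7–45 days. It gave 'No DMT' rates of 0.33, 0.27 and 0.20 for *q* = 25, 50 and 75%.

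**Study exit.** If half the triggered patients leave at relapse with no DMT recorded, *q* is in effect halved. With *d* = 14 the ratio rises from 0.80 to 0.90 (*q* = 25%) and from 0.59 to 0.80 (*q* = 50%). If all of them leave, it is 1.00.

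**Worked example.** Suppose 100 off-drug patients are each followed for 75 days, 8 of them relapse once, and 4 of those 8 then start a DMT.

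- All patients: 100 × 75/365.25 = 20.5 patient-years; 8/20.5 = 0.39.
- SAP 'No DMT': 96 × 75/365.25 = 19.7 patient-years; 4/19.7 = 0.20.
- Split at DMT start, with relapse mid-window and DMT 14 days later (51 off-drug days each for the 4): (96 × 75 + 4 × 51)/365.25 = 20.3 patient-years; 8/20.3 = 0.39.

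**Precision.** For an assumed 100 'No DMT' patients at 0.60 per year, 20.5 × 0.60 = 12.3 relapses are expected. The exact Poisson 95% interval for 12 events is about 0.30 to 1.02 per year.

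**The case against.** The strongest objection is that the link is not documented. The same protocol section also points to withdrawing from the study and switching, and a patient who leaves first and starts a DMT afterwards stays in 'No DMT' with the relapse counted, which adds no bias. The counselling text also suits patients still on study drug better than those already off it. This stands as a limit on size: nothing in the documents shows how often a relapse leads to a recorded DMT before end of study. It does not remove the route, because relapse visits and medication recording both run through follow-up.

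Second, every size above is assumed. The lowest ratios need no delay and a 75% trigger, which is hard to square with a relapse visit and an EDSS within 7 days. That also stands, and the ratios are illustrations only.

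Third, the table is exploratory, with no model, interval or contrast. At about 12 relapses, a 25% trigger with a 28-day delay moves roughly two of them, well inside the sampling error. This is why the point is minor. Imprecision is still not a reason to keep a rule whose error has a known direction and can be removed.

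Fourth, relapses and therapies are listed, so a reader could trace the timing. But 5.3.2.2 does not ask for DMT start in the relapse listing, and a listing or footnote would leave the displayed rate uncorrected.

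**Conclusion.** The point holds as a conditional bias of minor severity. The direction follows from the definitions alone: wherever an off-drug relapse leads to a recorded DMT before end of study, 'No DMT' is understated and 'Any DMT' overstated. The size depends on the trigger share, the delay and the proportion leaving the study, none of which the documents give. For 90-day follow-up, plausible inputs range from no effect to a material understatement. For 30-day follow-up after TP1 the effect is at most about 5% at a 14-day delay, but larger if DMTs start within a week. A small bias would be hidden by the imprecision of the rate. No confirmatory conclusion is affected; what is affected is how the 'No DMT' column reads as a measure of reactivation.

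**What to change.** For the post-treatment ARR only, add one table. Split each patient's relapses and person-time at the start date of the first DMT in use after ponesimod EOT, or censor there for the off-DMT rate, and assign each relapse by DMT status at onset. Keep the planned ever/never table beside it. State which date is used when the DMT start is partial: SAP 6.5 classifies such therapies, but 6.14 has no imputation rule for medication dates. Correct the Analysis Period wording in 5.3.2.2 at the same time.

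Keep the patient-level label for the lymphocyte and PFT tables, since they follow the same patients from baseline into follow-up. Add a footnote that it does not show DMT status on the sample date.

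The cost is SAP wording, one table and a little programming; the start date is already in SDTM.CM and named in 5.5.6. The downside is sparse cells, especially on-DMT time in TP1 discontinuers, and reliance on exact medication dates in a short window.
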